1.2. Rationale for the study

The estimation of dengue incidence is critical when designing an efficacy trial for a dengue vaccine. In a given city or region, dengue incidence is highly variable from one year to another (variations in geography, season, year-to-year variations in mosquito vector populations in different areas, etc.,) and cannot yet be predicted with sufficient accuracy in many locations being considered for clinical trials. In a dengue vaccine efficacy trial, volunteers are recruited from geographically defined sites. Some of these sites may experience high dengue transmission during the trial duration while others may have limited transmission. Therefore, making a valid assumption regarding the average incidence over time and across sites in order to assess the efficacy of an investigational vaccine is important.

In addition, a critical factor for the success of an efficacy trial is training staff at the various sites to perform study procedures such as febrile illness detection, dengue laboratory diagnosis and data collection in a cohort of subjects.

The proposed study will estimate the incidence of dengue infection and disease across geographically distinct locations in order to validate attack rate assumptions in future efficacy trials. We will enrol individuals from a random sample of households from selected communities of geographically different sites in Brazil and assess incidence of dengue infection and disease, by conducting scheduled serosurveys and an enhanced surveillance of febrile disease.

This study will also prepare potential sites for future clinical trials by setting up the logistics and training staff on site to enrol a cohort of subjects, perform dengue surveillance and other study procedures.

Finally, in line with the overarching strategy of building a strong partnership with the Ministry of Health (MoH), this study will serve as a useful comparison for evaluation of dengue surveillance systems

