7.2.2. Additional considerations

7.2.2.1. Incidence rate

In light of the low number of dengue episodes, the large number of positive anti-dengue IgG at visit 1 and the number of dengue cases reported outside the season,

1. The analyses of PCR confirmed cases (only 10 cases) and the analyses of secondary dengue infections were removed.
2. The analyses by seroprevalence at each visit were removed,
3. The analyses by season were removed. Only the analyses by calendar year are to be conducted

- 4. Subjects without seroprevalence status at visit 1 were removed from the ATP cohort because serological status of symptomatic/inapparent dengue infections cannot be assessed properly for such subjects
- 5. Planned analyses of medical and vaccination history were removed.
- 6. The statistical method was updated to ignore the household cluster effect and to provide incidence rate with confidence interval in absence of dengue episodes in a calendar year for a study site .

Regarding the last point, the expected annual incidence rate for a cohort of subjects followed over a full calendar will be computed using a log-linear model with the number of dengue events (all cases) as depend variable and the total number of subject-month as offset. The model will include the study site, year and month as independent categorical fixed effects (see below).

The expected annual incidence rate in a study site for each year will be estimated as the average of incidence rate over months

```

proc genmod ;
  class center month year;
  model evt= center year month /
    dist=poisson link=log offset=ln TYPE3;

  ods output Estimates=estimc;
  estimate 'center PPD 2014' intercept 12 center 12 0 0 0 0
    year 12 0 0 0 0
    Month 1 1 1 1 1 1 1 1 1 1 1;
  estimate 'center PPD 2014' intercept 12 center 0 12 0 0 0
    year 12 0 0 0 0
    Month 1 1 1 1 1 1 1 1 1 1 1;
  estimate 'center PPD 2014' intercept 12 center 0 0 12 0 0
    year 12 0 0 0 0
    Month 1 1 1 1 1 1 1 1 1 1 1;
  estimate 'center PPD 2014' intercept 12 center 0 0 0 12 0
    year 12 0 0 0 0
    Month 1 1 1 1 1 1 1 1 1 1 1;
  estimate 'center PPD 2014' intercept 12 center 0 0 0 0 12
    year 12 0 0 0 0
    Month 1 1 1 1 1 1 1 1 1 1 1;
  estimate 'overall 2014' intercept 12 center 2.4 2.4 2.4 2.4 2.4
    y 12 0 0 0 0
    Month 1 1 1 1 1 1 1 1 1 1 1;
  estimate 'center PPD 2015' intercept 12 center 12 0 0 0 0
    year 0 12 0 0 0
    Month 1 1 1 1 1 1 1 1 1 1 1;
  estimate 'center PPD 2015' intercept 12 center 0 12 0 0 0

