```

```

estimate 'overall' intercept 60 center 12 12 12 12 12
                        year 12 12 12 12 12
                        Month 5 5 5 5 5 5 5 5 5 5 5 5;
estimate 'overall center PPD' ' intercept 60 center 60 0 0 0 0
                        year 12 12 12 12 12
                        Month 5 5 5 5 5 5 5 5 5 5 5 5;
estimate 'overall center PPD' ' intercept 60 center 0 60 0 0 0
                        year 12 12 12 12 12
                        Month 5 5 5 5 5 5 5 5 5 5 5 5;
estimate 'overall center PPD' ' intercept 60 center 0 0 60 0 0
                        year 12 12 12 12 12
                        Month 5 5 5 5 5 5 5 5 5 5 5 5;
estimate 'overall center PPD' ' intercept 60 center 0 0 0 60 0
                        year 12 12 12 12 12
                        Month 5 5 5 5 5 5 5 5 5 5 5 5;
estimate 'overall center PPD' ' intercept 60 center 0 0 0 0 60
                        year 12 12 12 12 12
                        Month 5 5 5 5 5 5 5 5 5 5 5 5;

run;
    
```

```

data estimc; set estimc;
    if label='overall' or index(label,'overall center') then do;
        estimate=exp(lbetaestimate/60);
        lower=exp(lbetalowercl/60);
        upper=exp(lbetauppercl/60);
        end;
    else do;
        estimate=exp(lbetaestimate/12);
        lower=exp(lbetalowercl/12);
        upper=exp(lbetauppercl/12);
        end;
run;
    
```

In case of subgroup analysis by gender or by age at visit 1 (<=17years, 18-49 years and >= 50years) or in case the model does not allow estimating confidence interval (eg problem of convergence or situation where there is no event in a site, in a calendar year or in a month) CI will be computed using exact CI based on a Poisson Distribution.

The following case provides the SAS code for the exact CI for incidence rate per subject-year when there are 14 events and 400 subject-years:

```

data check;
    fu=400;
    n=14;
    Rate=n/fu;
    LL_rate= GAMINV(0.025, n)/fu;
    UL_rate= GAMINV(0.975, (n+1))/fu;
    LL_rate_=cINV(0.025, 2*n)/(2*fu);
    UL_rate_=cINV(0.975, 2*n+2)/(2*fu);
    
```

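### The site-by-year incidence rows come from a Poisson model without a site-by-year term, so if sites have different year patterns a local outbreak is understated and an empty site-year gets a positive rate

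*SAP*

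**What the plan says.** SAP Amendment 1, section 7.2.2.1, replaces the household-cluster method with a Poisson model with log link, coded as "model evt= center year month", with "the total number of subject-month as offset". In words: "The model will include the study site, year and month as independent categorical fixed effects". The output wanted is specific to site and year: "The expected annual incidence rate in a study site for each year will be estimated as the average of incidence rate over months". The code has 25 site-year ESTIMATE rows (five sites, 2014 to 2018). Each combines only the intercept, one site effect, one year effect and the averaged month effects.

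One declared purpose of the change is "to provide incidence rate with confidence interval in absence of dengue episodes in a calendar year for a study site".

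An exact Poisson interval is used for the gender and age subgroups, or when the model cannot give an interval. The examples given are a convergence problem or a "situation where there is no event in a site, in a calendar year or in a month". The exact limits are coded from gamma quantiles, for example "LL_rate= GAMINV(0.025, n)/fu".

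Protocol section 1.2 says that incidence in a given city varies strongly from year to year. Of the sites it says: "Some of these sites may experience high dengue transmission during the trial duration while others may have limited transmission".

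**The concern.** With site and year as main effects on the log scale, each site-year row is a site level multiplied by a year effect common to the whole study. The model can represent one site being higher than another, and one year being higher than another. It cannot represent a high year at one site that was ordinary elsewhere, which the protocol's rationale leads one to expect.

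The method was also chosen to handle empty site-years. Under this model an empty site-year takes its rate from the same site's other years and from other sites in that year. The fallback does not stop this, because it is tied to model failure or to a whole site, year or month without events.

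At stake are the site-by-year rows, which could inform attack-rate assumptions for future trials. Outbreak years may be read as milder than they were, and quiet ones as more active or even quieter.

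**Working it through.** The SAP states no site-year incidence to reproduce, so the check applies the model to known, assumed rates.

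**Inputs.** Covered site-years are taken from the table of covered seasons in SAP section 7: Rio and Manaus 2015–2018, Salvador 2016–2018, Natal 2017–2018, Campinas 2018 (14 in all). Person-time is 461.5 person-years per site-year, from protocol Table 15 (500 subjects, one year). It reproduces with 15% annual drop-out: 500 × 0.15 / (−ln 0.85) = 75 / 0.1625 = 461.5. *Assumed:* 3 per 1000 (the lowest planning rate) everywhere except Rio 2016 at 30; equal exposure in all months and no seasonality, so the month terms drop out.

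**Fit.** log(rate) = intercept + site + year, Poisson, fitted to expected counts (rate × 0.4615). Fitted rates per 1000, with assumed rates in brackets:

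| | 2015 | 2016 | 2017 | 2018 |
|---|---|---|---|---|
| Rio | 4.59 (3) | 22.94 (30) | 5.74 (3) | 5.74 (3) |
| Manaus | 1.41 (3) | 7.06 (3) | 1.76 (3) | 1.76 (3) |
| Salvador | – | 6.00 (3) | 1.50 (3) | 1.50 (3) |
| Natal | – | – | 3.00 (3) | 3.00 (3) |
| Campinas | – | – | – | 3.00 (3) |

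**Hand check.** A Poisson main-effects fit reproduces the site and year totals. With equal person-years this means the rates must sum alike.
- Rio: 4.59 + 22.94 + 5.74 + 5.74 = 39.01, against 3 + 30 + 3 + 3 = 39.
- 2016: 22.94 + 7.06 + 6.00 = 36, against 30 + 3 + 3 = 36.
- The fitted 2016:2018 ratio is 4.0 at Rio (22.94/5.74), Manaus (7.06/1.76) and Salvador (6.00/1.50). The assumed ratios are 10, 1 and 1.

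**Intervals.** The model interval for Rio 2016 is 13.1 to 40.1, which does cover 30.

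**Empty site-year.** Set Manaus 2016 to no cases and leave the rest unchanged. No site or year total is zero, so the fallback is not triggered by an empty site or year. The model gives Manaus 2016 as 5.1 (1.8 to 14.1). The SAP's exact formula gives 0, with upper limit −ln(0.025)/461.5 = 3.689/461.5 = 8.0 per 1000.

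**Sensitivity.**
- With month terms, and October–December 2014 added for Rio and Manaus (assumed), Rio 2016 is 22.7, Manaus 2016 is 7.3, and an empty Manaus 2016 is 5.4.
- In that layout, a smaller outbreak (Rio 2016 at 15) gives Rio 10.7, Manaus 5.5 and Salvador 4.8 in 2016.
- With no local outbreak, every cell returns 3.0.
- In the 14-cell layout with two outbreaks of 30 (Rio 2015, Manaus 2016), Rio 2016 is fitted as 15.0 (8.2 to 27.5) against 3, and Manaus 2016 as 15.0 (8.2 to 27.5) against 30. Here the intervals miss the assumed values.

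**How often the fallback would apply.** In 20,000 simulated Poisson data sets per scenario (2014 ignored), a whole site, year or month was empty as follows:

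| Scenario | Expected events | Flat months | 80% of cases in January–June (assumed) |
|---|---|---|---|
| One outbreak | about 32 | 71% | 95% |
| Two outbreaks | about 44 | 48% | 85% |

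**The case against.** The strongest reply is the fallback. The SAP itself cites a low number of episodes and only 10 PCR-confirmed cases. In the scenarios above an empty site, year or month occurs in 48% to 95% of simulated data sets, so the exact interval may often replace the model. This stands, and it limits what can be claimed: the total case count is not in the documents, so the route cannot be known. It does not remove the problem. The same table row may hold an observed or a borrowed result depending on the data. The fallback text also mentions only the interval, leaving the accompanying point estimate unclear.

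Second, the change is declared, the analyses are descriptive, and smoothing sparse data is a legitimate exchange of bias for precision. The primary objective is incidence by year or season in the study population, not by site and year, and the year totals are preserved. All of this is fair. But giving an empty site-year a rate and interval does not require a common year pattern, because the exact method already in the SAP does it. Amendment 1 plans no check of the assumption.

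Third, observed events and person-time may appear in the tables. Section 11.1 lists person-years among the displays, and the table templates are not part of the documents, so their absence cannot be asserted.

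A reader might go further and infer that the reported site-year incidences are wrong, or that quiet site-years are always inflated. The documents do not support either. If all sites share one year pattern, the estimates are unbiased by this route. In the illustration Campinas and Natal are fitted exactly, and Salvador 2017–2018 is pulled down, not up.

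**Conclusion.** The concern holds in conditional form. As specified, the model imposes one year pattern on all sites, against the protocol's own expectation. If site patterns differ, a local outbreak is understated where it occurred and cases are shifted between site-years, with site and year totals unchanged. One empty site-year does not by itself trigger the exact fallback and is then given a positive rate and a positive lower limit.

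The sizes shown (22.9 for 30, 7.1 for 3, 5.1 for 0) rest on assumed outbreak rates, equal person-time per covered site-year and flat months. A rate of 30 is twice the highest planning rate of 15. The figures show direction and plausible scale. They do not estimate the bias in this study, which cannot be determined from the documents.

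**What to change.** For the site-by-year rows, report observed events, person-years, the crude rate and the exact Poisson interval already coded in section 7.2.2.1. For zero events, set the lower limit to 0 explicitly, since the gamma quantile with shape 0 is undefined. Report no site-year estimate where a site had no follow-up: the code has rows for all five sites from 2014, while Campinas, for example, has 2018 as its only covered season. Keep the main-effects model for the overall rows, or show it beside the crude rates as a labelled smoothed supplement.

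Adding a site-by-year term to the model is less practical. About 97% of the simulated data sets contain at least one empty site-year, for which that term has no finite estimate.

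No new data are needed. Site-year intervals become wider: 14 events in 461.5 person-years give 14/0.4615 = 30.3 per 1000 with exact limits 16.6 to 50.9, against the model's 13.1 to 40.1 in the illustration. Crude rates for partly observed years are not put on a full-year basis, so those years should be flagged.

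### SAP 7.2.2.1 defines the site-year rate as the average of the monthly rates, but its code returns their geometric mean, so model-based levels fall below the SAP's own definition

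*SAP*

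**What the plan says.** SAP Amendment 1, section 7.2.2.1, replaces the household-clustered methods with a Poisson model ("dist=poisson link=log offset=ln TYPE3"). Site, year and month enter as main effects and subject-months form the offset. The target is the "expected annual incidence rate for a cohort of subjects followed over a full calendar" (the word year appears to be missing after this), and the definition for a site and year is: "The expected annual incidence rate in a study site for each year will be estimated as the average of incidence rate over months".

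In the code, each site-year ESTIMATE row gives the intercept, the site and the year a coefficient of 12 and each month a coefficient of 1. The data step then computes the rate in the line opening "estimate=exp(lbetaestimate/12" and the limits in the lines opening "lower=exp(lbetalowercl/12" and "upper=exp(lbetauppercl/12".

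The model is not used for gender and age subgroups, when it fails to converge, or in a "situation where there is no event in a site, in a calendar year or in a month". Those results use an exact Poisson interval around events divided by follow-up time.

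SAP section 8 makes all analyses descriptive. Protocol section 1.2 gives the purpose of the incidence estimates: "in order to validate attack rate assumptions in future efficacy trials".

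**The concern.** With a log link, a linear contrast averages log rates. Exponentiating that average gives a geometric mean, which cannot exceed the arithmetic mean and is strictly lower unless all twelve monthly rates are equal. The number of cases expected in a cohort followed for a full year is an arithmetic quantity, so the code and the definition disagree. SAP section 2.4 gives all five sites a January to June season, and sampling noise alone also makes fitted month effects differ.

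There are no hypothesis tests, so the rate and its interval are the result. Planning a vaccine trial needs the absolute level, which is the part the code moves. One report would also mix scales: model-based rows on the geometric scale, fallback and subgroup rows on the events-over-time scale.

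**Working it through.** The plan states no numerical result for this estimator, so there is no figure to reproduce. The check is algebra, then simulation.

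**1. Algebra.** Let η_m = intercept + site + year + month_m be the fitted log rate in month m, and λ_m = exp(η_m).

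- ESTIMATE row: 12·intercept + 12·site + 12·year + Σ month_m = Σ η_m
- Code: exp(Σ η_m / 12) = (λ_1 · … · λ_12)^(1/12), the geometric mean (GM)
- Text: (1/12) Σ λ_m, the arithmetic mean (AM)
- Ratio: GM/AM = exp(mean of month_m) / mean of exp(month_m)

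Site and year cancel because the model has no interaction with month. The factor is therefore the same for every site-year in a fit, and site or year rate ratios are untouched. With arbitrary coefficients, the code's formula gave 0.00073660, the GM 0.00073660 and the AM 0.00077896 (ratio 0.946).

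**2. Seasonality alone, no noise.** Let a share s of the annual rate fall evenly in January to June and the rest evenly in July to December. Monthly rates are then 2s·AM and 2(1−s)·AM, so GM/AM = 2√(s(1−s)).

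| s | GM/AM | If AM is 9.0 per 1000, the code targets |
|---|---|---|
| 50% | 1.000 | 9.0 |
| 60% | 0.980 | 8.8 |
| 70% | 0.917 | 8.2 |
| 80% | 0.800 | 7.2 |

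**3. Simulation, seasonality plus noise.** Inputs:

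- Seasons per site from SAP section 7: Rio 4, Manaus 4, Salvador 3, Natal 2, Campinas 1, so 14 site-years.
- Rates of 3 to 15 per 1000 person-years, from protocol section 8.2.3.
- Assumed: 500 subjects per month in each site-year (14 × 500 = 7000 person-years), equal true rates in all site-years, and the January to June shares.
- The model is skipped if any site, year or month has no event.
- At least 3000 fitted data sets per scenario. The chance that the model is used is an exact calculation.

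Each cell shows GM/AM where the model is used, with the chance that it is used in brackets.

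| Rate per 1000 | 50% | 60% | 70% | 80% |
|---|---|---|---|---|
| 3 | 0.880 (8%) | 0.874 (7%) | 0.861 (4%) | 0.838 (1%) |
| 6 | 0.881 (66%) | 0.869 (60%) | 0.833 (42%) | 0.777 (17%) |
| 9 | 0.905 (93%) | 0.888 (89%) | 0.836 (76%) | 0.754 (45%) |
| 12 | 0.929 (99%) | 0.908 (97%) | 0.844 (91%) | 0.745 (69%) |
| 15 | 0.943 (100%) | 0.921 (99%) | 0.856 (97%) | 0.746 (83%) |

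**4. Partial years.** The code also has a 2014 level. With 2014 limited to September to December at two sites and 2018 ending in August, model use at 9 per 1000 falls to 81/73/55/25%, while GM/AM stays at 0.897/0.882/0.835/0.758. With only November and December 2014, model use is 65/53/35/15% and GM/AM 0.894/0.882/0.834/0.762.

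**5. Intervals.** Coverage of the true annual rate by the SAP's 95% interval, averaged over the 14 site-years, is 96–97% at 3 per 1000, 96% at 6, 92–96% at 9, 88–95% at 12 and 85–95% at 15. The lowest single site-year is 81%, at 15 per 1000 with an 80% share. At 9 per 1000 the median ratio of upper to lower limit is 3.7 to 7.3.

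**The case against.** **Against the true rate, the code is not always low.** In data sets at 3 per 1000 where the model is used, the code's estimate averages 5–8% above the simulated truth, and an arithmetic mean would be 22–28% above it. At 6 per 1000 the code averages 0.91/0.90/0.88/0.84 of the truth, a deficit of 9–16% rather than the 12–22% measured against the AM. At 9 per 1000 the deficit broadly stands (0.92/0.90/0.85/0.77). This is correct and limits the claim. The cause is the fallback rule: at 3 per 1000 the model runs only on data sets with unusually many events, and the crude rate in those same data sets is inflated by 22–26%. Two distortions partly offset each other there; the geometric mean still departs from the SAP's definition.

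**The sizes are assumed.** At 50% and 60% shares, seasonality alone explains 0% and 2%; the rest of the simulated 6–13% is noise in the month effects. The documents give no support for shares of 70–80%, and the SAP cites cases outside the season as a reason to drop the seasonal analyses. Both remarks stand. They bear on size, not on whether text and code agree.

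**The harm is modest.** Average coverage falls below 90% only at 12 to 15 per 1000 with an 80% share, and the shift is smaller than the sampling error of one site-year. This stands, but the bias has the same factor in every site-year of a fit, so pooling does not average it out.

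**A reader could compare with the crude rate.** SAP section 11.1 lists person-years beside the incidence rate, so a crude rate can be recovered if event counts are shown too. That is a partial remedy. The factor itself cannot be recovered from the reported rate without the month effects.

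**Averaging on the link scale is a common convention, and the printed code may not be what was run**, since some rows use y where the model term is year. Neither point reconciles the text with the code, and nothing in the SAP says a geometric mean is meant.

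**Conclusion.** The concern holds, as something that should be fixed. Wherever the model is used and the fitted months differ, the site-year rate and both limits lie below the quantity the SAP defines. That direction is certain relative to the definition; it is not a claim that every reported rate is below the truth.

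The size rests on assumed monthly patterns and case counts. Where the model is used, it is about 10–25% at 9 per 1000 person-years and 6–25% at 15. At 3 per 1000 the model is rarely used, so the practical effect there is small. Site and year rate ratios, subgroup results and fallback results are unaffected. The overall rows also average logs over sites, years or both; their shift was not sized here.

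**What to change.** For each site-year, exponentiate the twelve fitted monthly log rates and then average them, or sum them for the annual rate. This puts the model rows on the same scale as the events-over-time fallback. Because the result is no longer a single linear contrast, take the interval from the delta method on the log scale or from a parametric bootstrap. In the same simulation the delta-method interval covered 95–96% on average at 6 to 15 per 1000. At 3 per 1000 (7000 person-years × 0.003 = 21 expected events) it covered about 93%, with 85% in the worst site-year, so a bootstrap is safer when events are few.

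Show the scaling in the code as well. The offset is subject-months, and section 11.1 reports per 1000 person-years, so a monthly rate needs a factor of 12 × 1000 = 12,000.

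If the geometric mean was intended, say so in the text and stop calling it the expected annual incidence rate.

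The cost is SAP wording and a few lines of SAS, including the delta-method or bootstrap step. No new data are needed.

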11. DATA DERIVATION RULES AND STATISTICAL METHODS

11.1. Data presentation

The following decimal description will be used for the analyses:

Display Table	Parameters	Number of decimal digits
Dengue cases	Incidence rate (in 1000 person-years) with LL & UL, person-years	1
Dengue cases	% of count, including LL & UL of CI	1
Dengue cases	Minimum, maximum, range	Number of decimals in the raw data
Dengue cases	Mean, median	Number of decimals in the raw data +1
Dengue cases	SD	Number of decimals in the raw data +2
Hematology/biochemistry	%	1
Demographic/baseline characteristics and changes between scheduled visits	Percentage, mean, median, standard deviation, minimum, maximum, Q1, Q3	1

CI = confidence interval

LL = lower limit of the confidence interval

SD = standard deviation

UL = upper limit of the confidence interval

Q1/Q3 = 25th and 75th percentiles

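### As written, the SAP's model code returns a geometric-mean rate per subject-month but labels it an annual incidence, at least 12-fold below the per-person-year scale when exposure is equal across months

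*SAP*

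**What the plan says.** SAP Amendment 1, section 7.2.2.1, replaces the household-clustered method with a log-linear model for event counts, with site, year and month as fixed effects and the "total number of subject-month as offset". In the code the offset appears only as a variable name: "dist=poisson link=log offset=ln TYPE3". How that variable is built is not shown.

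The target is described in one sentence: "The expected annual incidence rate in a study site for each year will be estimated as the average of incidence rate over months". The ESTIMATE statements for a site and year, or for all sites in a year, carry a total weight of 12. Those for all years carry a total weight of 60. The closing data step back-transforms them with "estimate=exp(lbetaestimate/12" and "estimate=exp(lbetaestimate/60" (each followed by a closing bracket), and treats both limits the same way.

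The same section sends gender and age subgroups, and any case where the model cannot give an interval, to an exact Poisson method. It introduces that method as "the SAS code for the exact CI for incidence rate per subject-year". Section 11.1 sets the display scale: "Incidence rate (in 1000 person-years) with LL & UL, person-years". Section 11.3.3 counts follow-up in days and obtains months by dividing by 12, or years by dividing by 365.25.

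**The concern.** Dividing a sum of twelve log rates by 12 undoes the summation; it does not annualise. If exposure is in subject-months, the exponentiated result is still per subject-month. The text has the same gap as the code, because an average of monthly rates remains a monthly rate.

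This is the only model specified for incidence by site and year, which is the primary objective, and section 9.1 sends the final analysis to the study report and to public posting. The study exists to check attack-rate assumptions for future efficacy trials. The protocol's planning range of 3 to 15 per 1000 person-years (section 8.2.3), divided by 12, becomes 0.25 to 1.25 on a display with one decimal. Subgroup and fallback rates would stay on the subject-year scale, so subgroups could look an order of magnitude above the overall rate they belong to.

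**Working it through.** **Reporting scale.** Protocol section 8.2.3 gives a 95% CI of 4.7 to 13.3 for 9 per 1000 person-years, with 3322.7 person-years and a design effect of 1.8. Check: 0.009 ± 1.96 × √(0.009 × 1.8 / 3322.7) = 0.009 ± 0.00433, that is 4.67 to 13.33 per 1000. It reproduces, so the planning scale is per 1000 person-years. The SAP prints no numerical result for its model.

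**What the contrast is.** Write λ(m) for the fitted rate in month m at a given site and year, per unit of offset. With twelve month coefficients (some lines as extracted show eleven, which may be an extraction artefact), the contrast is L = Σ log λ(m). Then exp(L/12) = (Π λ(m))^(1/12), the geometric mean of the twelve rates, still per unit of offset. The rows divided by 60 are the same kind of mean, taken over years as well.

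**Unit error alone.** Take the SAP's fallback example, 14 events in 400 subject-years:

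- Per subject-year: 14/400 = 0.0350 (exact limits 0.0191 to 0.0587).
- Per subject-month: 14/(400 × 12) = 0.00292. Ratio 12.
- Per unit of days/12: a year holds 365.25/12 = 30.44 units, so 14/(400 × 30.44) = 0.00115. Ratio 30.4.

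Fitting the SAP model to noise-free data (5 sites, 5 years, 12 months) at 35 per 1000 person-years, with equal monthly rates and true subject-months, the code gives 2.917 per 1000, with site-year limits 2.202 to 3.863. Multiplying by 12 gives 35.0 (26.4 to 46.4). The interval width depends on the cell sizes used; the factor 12 does not.

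**Adding the geometric mean.** Section 2.4 sets a January to June season at every site. Suppose six months have r times the rate of the other six, with equal exposure in each. The arithmetic mean over the geometric mean is (r + 1)/(2√r), and the shortfall is 12 times that. The values of r are assumptions.

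| r | (r + 1)/(2√r) | Code output × 1000 | Shortfall against 35.0 | Output × 12 × 1000 |
|---|---|---|---|---|
| 1 | 1.000 | 2.917 | 12.0 | 35.0 |
| 2 | 1.061 | 2.750 | 12.7 | 33.0 |
| 4 | 1.250 | 2.333 | 15.0 | 28.0 |
| 9 | 1.667 | 1.750 | 20.0 | 21.0 |

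**Other readings of the offset.** With days/12 taken literally, the shortfall runs from 30.4 (r = 1) to 50.7 (r = 9). With a subject-year offset it runs from 1.0 to 1.67: the unit error disappears and only the geometric-mean part remains.

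**The case against.** The strongest reply is that the documents do not settle the unit. `ln` is undefined and section 11.3.3 allows conversion to years. The annual label, the display scale and the fallback all point to years; one phrase points to months. If `ln` held log subject-years, the unit error would vanish. Also, neither code block multiplies by 1000 although the display is per 1000, so some scaling happens in programs or table shells not shown, and a multiplication by 12 could be there too. The listing looks unfinished: a few ESTIMATE lines name an effect `y` that is not in the model. All analyses are descriptive, and person-years are to be displayed, so a gross discrepancy could be noticed.

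This limits what can be claimed. A reader might infer that every reported model rate is exactly 12 times too low, or that final results are in error by that factor. The documents support neither. Exactly 12 needs equal monthly rates and true months, and the production code is not visible.

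What remains is that the SAP's explicit statement of the offset is subject-months, and a subject-year reading contradicts it. A scaling by 1000 applied to both routes would leave them apart, and no step specific to the model rows is specified. Followed as written, the rule gives a monthly rate.

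**Conclusion.** The point holds as an error in the written method: a geometric-mean rate per subject-month is presented as an annual incidence, next to fallback rates per subject-year. The unit error is a factor of exactly 12 on estimates and limits with true calendar months, or 30.4 under the literal rule in section 11.3.3. Against the arithmetic annual rate the shortfall is at least 12-fold and rises with seasonality, to 20.0 at an assumed ratio of 9. That lower bound supposes equal exposure across months. With uneven exposure, a crude rate weights the months differently and the ratio shifts.

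The verdict rests on `ln` being log subject-months and on no unseen step rescaling only the model rows. It is also tempting to conclude that multiplying by 12,000 cures the problem. That repairs the unit only: a true 35.0 would still appear as 33.0, 28.0 or 21.0 at ratios of 2, 4 and 9.

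**What to change.** - Define `ln` explicitly, either as log subject-years (days/365.25) or as log true subject-months. Correct the days-to-months divisor in section 11.3.3; the superseded June 2019 SAP (section 12.4.3) used 30.4375.
- With a subject-month offset, obtain the annual rate as the sum of the twelve back-transformed monthly rates. With a subject-year offset, use their arithmetic average. Either replaces the exponential of the mean log rate.
- Derive limits for that quantity by the delta method, using the model's covariance matrix, or by bootstrap. Exponentiating the existing contrast limits will not do.
- Apply the same correction to the rows divided by 60, and state how sites and years are weighted in the overall rows.
- Multiply rates and limits by 1000 on both the model and fallback routes, so that all rows are per 1000 person-years.
- Reword the sentence that defines the annual rate so that it matches.

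The cost is a definition, a few sentences of SAP text and a modest rewrite of the post-processing step. No new data are needed. Checking each model rate against crude events over person-years would show whether the scale is right.
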